3.4.2 Secondary Study Endpoints

The secondary endpoints will be to determine absolute and percent changes in airway size using different decide configuration settings and to determine the degree to which changes in airway size correlate with changes in sleep study parameters including AHI and ODI.

4 Study Population and Duration of Participation

The study population includes male and female patients over the age of 18 who have undergone Inspire UAS implantation to treat moderate to severe OSA.

4.1 Duration of Study Participation

Participation is estimated to last 4-6 weeks and will occur during routine clinical follow up appointments.

4.2 Total Number of Subjects and Sites

All eligible patients undergoing Inspire implantation by the primary investigator during a 2-year period will be recruited. This is estimated to amount to up to 50 eligible patients at the University of Pennsylvania.

4.4 Exclusion Criteria

- Significant central sleep apnea
- Presence of other sleep disorders
- History of neurologic or neuromuscular disease
- Historical or present substance abuse
- Bleeding disorders
- Autoimmune diseases that increase risk of nasal trauma such as Wegener's, Sarcoidosis, etc.
- Pregnancy

4.5 Subject Recruitment

Subjects will be identified using the surgical log of the principal investigator. All patients who have recently undergone device implantation by the principal investigator and are presenting for device activation will be recruited to the study.

4.6 Vulnerable Populations:

Children, pregnant women, fetuses, neonates, or prisoners are not included in this research study. Pregnancy status will be determined based on patient report; and that if a patient becomes pregnant during the study, the subject will be removed from the study and will resume receiving standard care for sleep apnea. Students or employees of Penn will be informed that their decision to participate will not affect their standing with the University in any way.

5 Study Procedures

See below and Table 1.

CONFIDENTIAL

5.1 Screening

- Medical records review to determine that patients meet inclusion criteria and do not meet exclusion criteria
 - Includes: medical history, age, allergies, BMI, prior sleep studies, and Inspire device usage report from last Sleep Clinic visit

5.2 Study Intervention

5.2.1 Visit 1: Otolaryngology Clinic for Awake Endoscopy

- Informed consent
- Vital signs: HR, RR, BP, SpO₂, BMI
- Targeted Head and Neck Physical Exam
 - Tongue size, lateral peritonsilar narrowing, palate shape, Modified Mallampati score
- Recorded exam of awake endoscopy at rest and with standardized configurations detailed in section 3.3 (Attachment 1)
 - Measurement and analysis of airway size to be completed by single co-investigator between Visits 1 and 2. Configuration resulting in greatest airway size will be used as test configuration during Visit 2 sleep study.

5.2.2 Visit 2: In-lab Sleep Study

- Polysomnography
 - Half of study using standard implant configuration, half of study using test configuration determined by awake endoscopy.

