the study team to formally measure and analyze airway size in the various conditions after this visit and the “optimal” test configuration will be determined based on airway measurements. Subjects subsequently will undergo an in-lab sleep study for titration of their device (Visit 2). Titration sleep study will ensue with the Inspire device in A) the standard (+++) configuration and B) the “optimal” test configuration. Voltage used with each implant configuration may be increased to achieve effective reduction in AHI at the discretion of the sleep physician; this is routinely performed during titration polysomnography in our current clinical practice. At the end of the sleep study, the device will be returned to the standard setting until further follow up with their sleep medicine physician. This concludes the subject’s participation in the study. Subjects will obtain the results of the sleep study and discuss further device management with their sleep medicine physician during routine follow up.

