3.3 Study Measures

Awake endoscopy will be performed during Visit 1 during which airway size will be video recorded at rest with implant off and with a standardized sequence of implant configurations that were determined by Inspire Corporation during pre-market testing including +++, ---, o-o, -o-, and -+-+. These settings will be tested to determine the voltage at which patients sense tongue movement (sensation threshold) and the voltage at which the tongue is visualized protruding from rest past the teeth (functional threshold). The different electrode configurations will then be tested at various voltages above the subject’s measured functional thresholds.

Measurements of cross-sectional, anterior-to-posterior, and lateral airway size in the retropalatal and retroglossal regions will be taken from recorded endoscopic exams using the image analysis program Amira by Visage Imaging (Richmond, Victoria, Australia). Measurements will take place between Visits 1 and 2. Standard AHI and ODI measurements will take place during in-lab sleep study (Visit 2). Efficacy of awake endoscopy to determine optimal device configuration will be assessed by comparing cross-sectional airway size (retropalatal and retroglossal), AHI and ODI with the standard device configuration compared to airway size, AHI and ODI with the test configuration. In patients for whom the standard configuration (+++) results in greatest airway size, this will be the sole configuration tested during sleep study, and identical values for airway size, AHI, and ODI will be used in analysis comparing the standard configuration with the “test” configuration.

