5.5 Efficacy Evaluations

Efficacy of the intervention being tested (awake endoscopy to determine optimal Inspire device configuration) will be assessed by comparing AHI and ODI using the standard device configuration compared to AHI and ODI with the test configuration. The intervention will be deemed efficacious if a statistically significant reduction in AHI and/or ODI is achieved with the test configuration determined using awake endoscopy compared to the standard device setting.

CONFIDENTIAL

6 Statistical Plan

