6.1 Sample Size and Power Determination

We estimate enrollment of roughly 30-40 patients. This is a pilot study since there has been no similar attempt at using and validating awake endoscopy for implant activation. Sample size and power calculations for paired t-test indicate that ~30 subjects would yield a study that is powered to detect a 50% effect size (using a standard $\alpha=0.05$, $\beta=0.2$). Additional subjects would enable detection of a smaller effect size.

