6.2 Statistical Methods

Analysis of all outcomes will be performed at the completion of the study. In the analysis of the primary outcome of interest, paired t-tests will be used to compare differences in AHI and ODI using the test Inspire device configuration and the standard device configuration. Paired t-tests will also be used to analyze whether significant differences in airway size exist using different device configurations: namely, the “test” configuration that has the largest airway size compared to the standard device configuration. A Pearson correlation test will be used to determine whether changes in airway size using standard and test configurations correlate with changes AHI and changes in ODI.

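### Nothing sets or randomises which configuration runs first on the split sleep-study night, so half of night can be confounded with configuration in the primary AHI/ODI comparison

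*Combined protocol and SAP*

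**What the plan says.** All references are to the combined protocol and SAP.

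- **Layout of the night.** Section 5.2.2: "Half of study using standard implant configuration, half of study using test configuration determined by awake endoscopy". Section 3 (Investigational Plan) introduces the session with "Titration sleep study will ensue with the Inspire device in A) the standard (+++) configuration", then names the test configuration as item B. Neither place says which runs first.
- **End of the night.** Section 3: "At the end of the sleep study, the device will be returned to the standard setting", pending follow-up with the sleep physician.
- **Titration.** Section 3: "Voltage used with each implant configuration may be increased to achieve effective reduction in AHI at the discretion of the sleep physician".
- **Subjects whose best configuration is the standard one.** Section 3.3: "this will be the sole configuration tested during sleep study, and identical values for airway size, AHI, and ODI will be used in analysis". Their paired difference is therefore zero.
- **Bias control.** The heading text of section 6.3 mentions randomisation and blinding. The two measures listed are recruitment of all eligible subjects and blinded measurement of airway size. Neither concerns the sleep study.
- **Primary analysis.** Section 6.2: "paired t-tests will be used to compare differences in AHI and ODI using the test Inspire device configuration and the standard device configuration". Section 6.3.2 repeats this. No period or order term appears.
- **Success rule.** Section 5.5 declares the intervention efficacious if a "statistically significant reduction in AHI and/or ODI is achieved with the test configuration".

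**The concern.** In a within-subject comparison where each configuration occupies one half of the night, anything that differs between the halves enters the paired difference unless the order varies between subjects. The protocol contains one possible source itself: voltage may be raised during the night, so the half run second may follow more titration than the half run first.

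Both primary outcomes come from the same two half-nights, and section 5.5 attaches the efficacy verdict to them. A shift favouring the test configuration can produce a significant reduction with no configuration effect behind it. A shift the other way can hide a real benefit. Section 6.1 notes that "Additional subjects would enable detection of a smaller effect size", but more subjects also make a spurious shift of the same size more likely to reach significance.

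If one order is used throughout, the problem cannot be repaired after data collection, because a period term would be fully aliased with configuration.

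**Working it through.** **Inputs from the documents.** About 30 subjects, planned enrolment 30-40, α = 0.05, β = 0.2 and a 50% effect size (section 6.1); paired t-test (6.2, 6.3.2); zero differences for standard-best subjects (3.3).

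**Assumptions.** The 50% effect size is read as 0.5 SD of the paired difference, and α as two-sided. The half-of-night shift and the share of subjects tested on both configurations are not given, so both are ranged. Rates are per endpoint.

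**1. The plan's own figure.** n = ((z₀.₉₇₅ + z₀.₈₀)/d)² = ((1.960 + 0.842)/0.5)² = 31.4, so 32, which is consistent with about 30. The exact paired t-test needs 34; at n = 30 its power is 75.4%.

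**2. Where the shift goes.** Let D = (value on standard) − (value on test), so that positive means a reduction with test. Let δ be the configuration effect and π the fall from first half to second half.

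- Standard first: E[D] = δ + π
- Test first: E[D] = δ − π

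If everyone is standard-first, the paired t-test estimates δ + π. With m of n subjects tested on both and the rest entered as zero, it estimates (m/n)(δ + π): diluted, but not corrected.

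**3. No true effect (δ = 0), standard always first, shift favouring test.** With m = n the test statistic is noncentral t with n − 1 df and noncentrality π√n. For example, at π = 0.25 and n = 30 this is 0.25 × 5.477 = 1.37. Cells with m < n were simulated with 200,000 runs each. The table shows the rate of a significant reduction, nominally 2.5%.

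| n | tested on both (m) | π = 0.1 | π = 0.25 | π = 0.5 |
|---|---|---|---|---|
| 30 | 30 | 8% | 26% | 75% |
| 30 | 24 | 7% | 21% | 65% |
| 30 | 21 | 6% | 19% | 58% |
| 30 | 15 | 5% | 14% | 43% |
| 40 | 40 | 9% | 34% | 87% |
| 40 | 20 | 6% | 18% | 56% |

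At π = 0.1 and n = 30, two-sided rejection (nominal 5%) is 8%, 7%, 7% and 6% for m = 30, 24, 21 and 15.

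**4. Shift against test.** With no true effect and n = m = 30, the rate of a significant reduction falls to 0.64%, 0.05% and 0% at 0.1, 0.25 and 0.5 SD. With a true 0.5 SD benefit and an opposing 0.25 SD shift, the net mean is 0.5 − 0.25 = 0.25 SD. At n = 30, power therefore drops from 75%, 65%, 58% and 43% to 26%, 21%, 19% and 14% for m = 30, 24, 21 and 15.

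**5. Order randomised 1:1 with a period term.** The average of the two sequence means is ((δ + π) + (δ − π))/2 = δ. Under a 0.5 SD shift at n = 30, simulated two-sided type I error is 5.0%, 5.0%, 5.0% and 4.8% for m = 30, 24, 21 and 15. Power at δ = 0.5 is 75%, 65%, 58% and 43%, essentially that of the planned test with no shift. The number needed for 80% power stays at 34.

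Balancing the order without the period term is unbiased but conservative. At n = m = 30 with a 0.5 SD shift, type I error is 2.9% and power 67%.

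**6. What remains after the change.** If titration carries over only in standard-first subjects, by c, the adjusted estimate is biased by c/2. False rejection (two-sided) at c = 0.25 and 0.5 SD is 10% and 26% with m = 30, 9% and 22% with 24, 8% and 19% with 21, and 7% and 15% with 15. Without the change the same carry-over gives 26% and 75% with m = 30.

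**The case against.** The documents do not say that the order is fixed. The A and B labels may simply name two configurations, and the return to standard at the end of the night is tied to later follow-up, so it says little about which half came first. If the order varied between subjects without a pattern, full aliasing would not occur. The rates in steps 3 and 4 are conditional on a constant order and an assumed shift. The largest cells need a nuisance shift as big as the design effect, and at 0.1 SD the inflation is modest. Titration is allowed under both configurations, and nothing states that a voltage reached in one half carries into the other. The study also calls itself a pilot.

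Most of this stands as a limit on strength. The bias is possible, not shown; its size and direction are unknown; and the titration route is an inference. None of it supplies the missing safeguard. An order left to the night's convenience is neither known to be balanced nor required to be recorded, and the planned test would not adjust for it. Pilot status does not help either, because section 5.5 still declares efficacy on statistical significance.

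**Conclusion.** The concern holds and should be fixed before Visit 2 data are collected. For subjects tested on both configurations, the order is neither specified nor randomised, and the primary analysis cannot separate configuration from half of night if the order is constant.

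The case rests on the unprotected primary comparison, not on any single cell of the table. The per-endpoint rates are also not the study's overall false-claim rate, because section 5.5 accepts success on either AHI or ODI.

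**What to change.** **Sections 3 and 5.2.2.** For every subject whose test configuration differs from standard, randomise the order 1:1 (standard first or test first) in permuted blocks, after airway measurement and before Visit 2. Have the sleep lab record the order actually used and any departure.

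**Section 6.2.** In those m subjects, regress the paired difference in AHI, and separately in ODI, on a sequence code of +1/2 or −1/2. The intercept is the period-adjusted configuration effect, with m − 2 df. To keep the all-subject comparison of section 3.3, report (m/n) × this effect, with its confidence interval scaled by m/n and the same test. For example, with m = 24, n = 30 and an effect of 0.5 SD, the all-subject effect is 0.8 × 0.5 = 0.40 SD, with a half-width of 0.8 × 2.074/√24 = 0.34 SD. If the two-configuration subset is also reported, label it as a separate estimand.

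**Limitation to state.** Randomised order halves the bias from one-directional titration carry-over but does not remove it.

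**Cost.** A short amendment, a randomisation list and one degree of freedom, with no extra visit or procedure and no change to any voltage or treatment rule. There are two drawbacks. Visit 2 is also the routine titration night, so the lab must work to an assigned order. The scaled interval treats the observed share of two-configuration subjects as fixed.

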5.3 Unscheduled Visits

Patients will be given information to contact the research team in case there are any concerns that arise. They will also be allowed to schedule appointments with the research team to discuss any issues in person.

5.4 Subject Withdrawal

Patients may withdraw from the study for any reason with no explanation or excuse required. They may do this without impact to their care. They may also be removed from the study at the discretion of the PI for lack of adherence to intervention, to visit schedules, adverse events, or due to changes that may result in alteration of sleep architecture. This includes significant weight loss or weight gain, ablative or orthognathic upper airway surgery, trauma, neoplasm of head and neck, autoimmune disease affecting airway, substance abuse, or initiation of medication that may alter sleep architecture prior to completion of the study.

5.4.1 Data Collection and Follow-up for Withdrawn Subjects

Subjects who withdraw from the study may withdraw at any time. Follow up visits are not necessary as there will be no study material to be collected.

5.5 Efficacy Evaluations

Efficacy of the intervention being tested (awake endoscopy to determine optimal Inspire device configuration) will be assessed by comparing AHI and ODI using the standard device configuration compared to AHI and ODI with the test configuration. The intervention will be deemed efficacious if a statistically significant reduction in AHI and/or ODI is achieved with the test configuration determined using awake endoscopy compared to the standard device setting.

CONFIDENTIAL

6 Statistical Plan

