9.2	AUDITING AND INSPECTING.....	14
10	ETHICAL CONSIDERATIONS	14
10.1	RISKS	14
10.2	BENEFITS	14
10.3	RISK BENEFIT ASSESSMENT.....	14
10.4	INFORMED CONSENT PROCESS / HIPAA AUTHORIZATION	15
11	STUDY FINANCES	15
11.1	FUNDING SOURCE.....	15
11.2	CONFLICT OF INTEREST	15
11.3	SUBJECT STIPENDS OR PAYMENTS	15
12	PUBLICATION PLAN	15
13	REFERENCES	15
14	ATTACHMENTS	16
15	APPENDICES	16
15.8	SOURCE DOCUMENTS	16
15.9	CASE REPORT FORMS (CRFs).....	17

CONFIDENTIAL

This material is the property of the University of Pennsylvania.

Study Summary

Title	Prospective Use of Awake Endoscopy to Direct Inspire Therapy for Obstructive Sleep Apnea
Short Title	Awake Endoscopy for Inspire
IRB Protocol Number	828956
Methodology	Validation cohort study
Study Duration	2 years
Study Center(s)	Single-center (University of Pennsylvania)
Objectives	
Primary:
 
• To determine the usefulness of awake endoscopy during activation of Inspire device 
Secondary:
 
• To determine optimal configuration of the Inspire upper airway stimulator by quantifying changes in upper airway size for multiple implant configurations• To correlate changes in airway size on endoscopy with sleep study outcomes
Number of Subjects	30-40
Main Inclusion Criteria	
• Patients with moderate to severe OSA• Recipient of Inspire Upper Airway Stimulation Implant surgery• Age 18 or above
Intervention	Awake endoscopic exam will be performed to measure airway size in the retropalatal and retroglossal upper airway regions using different Inspire implant configurations and voltages. The optimal test configuration determined on endoscopy will be tested during a sleep study and compared to the standard-of-care device configuration, with improvements in sleep study outcomes indicating that awake endoscopy is useful during Inspire implant activation.
Statistical Methodology	Paired t-tests will be used to compare differences in AHI and ODI using the test Inspire device configuration/voltage with the standard device configuration/voltage. Paired t-tests will also be used to analyze whether significant differences in airway size exist using different device configurations and voltages. A Pearson correlation test will be used to determine whether changes in airway size correlate with changes AHI and changes in ODI.

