3.4 Study Endpoints

3.4.1 Primary Study Endpoint

The primary endpoint is to assess the efficacy of awake endoscopy in determining optimal implant configuration during implant activation. A decrease in AHI and ODI with test configuration compared to standard configuration will indicate that awake endoscopy is useful for identifying optimal implant configuration compared to the current method of activation without endoscopy.

CONFIDENTIAL

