6.3.2 Analysis of Primary Outcome of Interest

A paired t-test will be used to compare differences in AHI and ODI using the test configuration compared to the standard device configuration.

7 Safety and Adverse Events

All subjects entered into the study will have detailed information collected on adverse events for the overall study safety analysis.

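### The primary success rule is stated in conflicting ways: section 5.5 accepts a significant fall in AHI or ODI, section 3.4.1 asks for a fall in both with no test

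*Combined protocol and SAP*

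**What the plan says.** The protocol describes success on the primary endpoint in three places.

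- Section 5.5 (Efficacy Evaluations): "The intervention will be deemed efficacious if a statistically significant reduction in AHI and/or ODI is achieved with the test configuration". One significant result out of two is enough.
- Section 3.4.1 (Primary Study Endpoint): "A decrease in AHI and ODI with test configuration compared to standard configuration will indicate that awake endoscopy is useful". Both measures must fall, and no test is mentioned.
- Study Summary, Intervention row: "with improvements in sleep study outcomes indicating that awake endoscopy is useful during Inspire implant activation". Neither the measures nor a test are specified in that row.

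The statistical sections do not settle the matter. Section 6.2 states: "In the analysis of the primary outcome of interest, paired t-tests will be used to compare differences in AHI and ODI". Section 6.3.2 repeats it in the singular: "A paired t-test will be used to compare differences in AHI and ODI using the test configuration". Neither section ranks the two measures, says how two results combine, or adjusts for testing twice.

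Section 6.1 gives one calculation: "Sample size and power calculations for paired t-test indicate that ~30 subjects would yield a study that is powered" for a 50% effect size with alpha 0.05 and beta 0.2. It does not say which measure was sized or whether the test is one- or two-sided.

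**The concern.** The success rule determines what the trial will conclude, and here two rules can return different answers from the same data:

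- AHI falls with p=0.20 and ODI falls with p=0.30. Section 3.4.1 is met; section 5.5 is not.
- ODI falls with p=0.04 and AHI rises. Section 5.5 is met; section 3.4.1 is not.

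All outcomes are analysed at the end of the study, so if the rule is not fixed beforehand it can be picked with the results in hand.

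Two further problems follow. Read literally, 3.4.1 is often met by chance, because it asks only for two means to move in the same favourable direction. Section 5.5, for its part, gives two unadjusted opportunities for a significant reduction, while section 6.1 budgets a single alpha of 0.05 for one test.

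**Working it through.** **Inputs.** From section 6.1: n=30, alpha 0.05, power 80%, effect size 50%, read here as a mean paired difference of 0.5 SD (an assumption). Applying 0.05 to each measure separately is inferred, since no split is given. Sidedness is not stated, so both are shown. The correlation r between the AHI and ODI differences is not given; r from 0 to 0.9 is assumed. Paired differences are taken as normal.

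**Step 1: the plan's own figure.** For one paired test, n = ((z for alpha + z for power)/0.5)².

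- Two-sided: ((1.960 + 0.842)/0.5)² = 31.4, so 32, close to the stated 30.
- Exact noncentral t, two-sided: 34 patients for 80%; power at n=30 is 75.4%.
- One-sided: 24.7, so 25 by the normal formula and 27 by exact t; power at n=30 is 84.8%.

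The stated figure is thus a calculation for one test. It covers neither an either-or rule nor a both-significant rule.

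**Step 2: chance success under 3.4.1 read literally.** With no effect, the probability that both means fall is 1/4 + arcsin(r)/(2π).

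**Step 3: two chances under 5.5.** With independent two-sided tests, the chance of at least one false significant reduction is 1 − 0.975² = 4.9%, against 2.5% for one test. With one-sided 0.05 tests it is 1 − 0.95² = 9.75%, against 5%. Simulation covers the correlated cases.

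**Step 4: how often the rules disagree.** Two correlated paired t-tests were simulated at n=30, with at least 200,000 runs per cell. Tests are two-sided 0.05 unless marked.

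| Quantity | r=0 | r=0.5 | r=0.8 | r=0.9 |
|---|---|---|---|---|
| No effect: literal 3.4.1 met | 25% | 33% | 40% | 43% |
| No effect: 5.5 met | 4.9% | 4.5% | 3.9% | 3.5% |
| No effect: 5.5 met, one-sided 0.05 | 9.8% | 8.8% | 7.5% | 6.8% |
| Opposite verdicts, no effect | 25% | 30% | 36% | 39% |
| Opposite verdicts, 0.25 SD on both | 47% | 47% | 53% | 56% |
| Opposite verdicts, 0.5 SD on both | 6% | 11% | 16% | 18% |

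Counting significant results in either direction, the two-sided family-wise rate is 9.7% at r=0 and 7.0% at r=0.9.

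**Step 5: the charitable reading.** Suppose 3.4.1 borrows significance from 6.2, so that both measures must be significant. At 0.5 SD on each:

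| Rule | r=0 | r=0.5 | r=0.8 | r=0.9 |
|---|---|---|---|---|
| Either significant (5.5) | 94% | 89% | 84% | 81% |
| Both significant | 57% | 62% | 67% | 70% |
| Difference = disagreement | 37% | 26% | 17% | 12% |

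With no effect, disagreement on this reading falls to 2–5%.

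**Step 6: identical values.** Section 3.3 enters equal values when the standard configuration gives the largest airway. If 30% or 50% of differences are zero, the two-sided false-reduction rate under 5.5 is 3.5–4.8% or 3.5–4.6%, so step 3 hardly changes.

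**The case against.** The strongest reply is that 3.4.1 is a statement of intent. It says what a decrease would indicate, 5.5 gives the operative rule, and 6.2 supplies the test. On that view the high chance-success figures come from an unduly literal reading. Part of this stands: the 25–43% and the null disagreement of 25–39% are the literal extreme, and they shrink to 2–5% if significance on both is implied. But no text makes 5.5 override 3.4.1, and *and* against *and/or* still separates the verdicts in 12–37% of trials at 0.5 SD.

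It can also be said that both sentences give sufficient conditions, neither saying *only if*, so they do not strictly contradict each other. That reading makes matters worse. Success would then follow from meeting either rule, which with no effect happens in about 25% + 2% = 27% of trials at r=0 and 43% at r=0.9.

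Three narrower points are fair:

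- The case of one measure significant while the other rises is rare when AHI and ODI move together: about 2.4% of null trials at r=0, 0.5% at r=0.5 and 0.02% at r=0.8. The common conflict is both falling without significance.
- With two-sided tests, the false-reduction rate under 5.5 stays just under 5%. The higher family-wise figure counts significant worsening, which 5.5 does not treat as success. Multiplicity alone would be a modest point.
- Section 6.1 calls this a pilot. That softens the consequence, but the same section sets alpha and power, and 5.5 commits to an efficacy verdict.

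**Conclusion.** The concern holds. The primary decision rule is contradictory as written, and nothing in the document reconciles it; this must be fixed before data are seen. Depending on the reading of 3.4.1, the two rules disagree in 6–18% (literal) or 12–37% (significance implied) of trials at 0.5 SD. With no effect the ranges are 25–39% and 2–5%. The unadjusted second test is secondary: it raises the false-reduction rate to 3.5–4.9% from 2.5% two-sided, or to 6.8–9.8% from 5% one-sided.

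These sizes rest on n=30, normal differences, an assumed correlation of 0 to 0.9, 0.05 applied to each test, and the 50% effect size meaning 0.5 SD. That the rules conflict depends on none of these assumptions.

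**What to change.** State one rule, with its sidedness, and use it in the Study Summary and sections 3.4.1, 5.5, 6.2 and 6.3.2. Possible text for 5.5:

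> Awake endoscopy will be declared efficacious if mean AHI is significantly lower under the test than under the standard configuration (paired t-test, two-sided alpha 0.05). ODI will be tested at two-sided alpha 0.05 only if the AHI reduction is significant.

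Section 3.4.1 and the Study Summary should then refer to 5.5. Testing in this order keeps the family-wise error at 0.05 without splitting alpha. Putting AHI first is a choice, because the document treats the two measures equally; the sponsor may put ODI first, provided the order is fixed in advance. Section 6.1 should say which measure and which sidedness its figure of about 30 refers to.

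**Cost.** Mostly wording, plus some chance of success, since a claim on the second measure alone is no longer possible. At 0.5 SD and two-sided 0.05, n=30 gives about 75% on one primary measure, against 94%, 84% and 81% under the either-or rule at r=0, 0.8 and 0.9. That is below the planned 80%; 34 analysed patients give 81%, within the planned 30–40. A one-sided 0.05 test at n=30 gives 85%.

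These power figures hold only if 0.5 SD already averages over patients with identical values under section 3.3. If 0.5 SD applies only to patients whose configuration differs, and 30% are zeros (both assumptions), power is about 58% at n=30, 64% at 34 and 72% at 40.

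If the sponsor prefers to keep an either-or rule, a Bonferroni split (two-sided 0.025 each) needs 41 patients for 80% power on one measure, just above the planned range.
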